### g. Shockwave and calcaneal spur:

The primary effect is the direct mechanical forces that result in the maximal beneficial pulse energy concentrated at the treatment site. in addition to that, the secondary effect is the indirect mechanical forces by cavitation, which may cause negative effect or damage to the tissues which can help in calcaneal spur destruction (Wang, 2012)(Frairia & Berta, 2011) (Schmitz C et al., 2013)

Xian Li et al., conducted meta-analysis research compared the effectiveness of eight modalities for treating plantar fasciitis (Shockwave therapy), both Intracorporeal pneumatic shock therapy (IPST) and extracorporeal shock therapy (FSWT (3 groups low, medium, high energy flux density), RSWT), Low level LASER therapy, Ultrasound therapy (US), and noninvasive interactive neurostimulation (NIN) ultrasound-guided pulsed radiofrequency (UGPRF) treatment were included. The therapies compared these modalities with each other or with a sham group. Regarding the three follow up effectiveness time points, RSWT provided relatively

more effective and stable pain relief compared with other modalities. Consequently, RSWT is a promising candidate for clinical applications. FSW therapies and US can also be considered treatment candidates. However, H-FSW and UGPRF not recommended (**X. Li et al., 2018**).

### **3. Calcaneal spur and Acetic acid:**

An acetic acid gel is an important component used via ultrasound phonophoresis to treat bone calcification deposits. It is composed of calcium carbonate ( $\text{CaCO}_3$ ) which exposed to active acetate radical and replace the carbonate forming the blood soluble calcium acetate molecule  $\text{Ca}(\text{CH}_3\text{COO})^2$  (**Pamplona et al., 2017**).

Shtofmakher G et al., describe that the use of acetic acid as ionized solution to treat insertional Achilles tendonitis (Calcaneal exostoses of the Achilles tendon) pain. They claim that a significant improvement in pain and function as the acetic acid helps to convert exostoses composed of calcium carbonate ( $\text{CaCO}_3$ ) to more chemically active acetate radical and replace the carbonate forming the blood soluble calcium acetate molecule  $(\text{Ca}(\text{C}_3\text{H}_3\text{O}_2)_2)$ . In another study by Japour et al., they describe that transdermal application of acetic acid through iontophoresis was shown to be an effective conservative treatment modality for heel pain. (**Kilfoil et al.,2014**).

The use of acetic acid iontophoresis treatments for chronic heel pain has shown promising results within 3–4 weeks and over an extended follow up period of greater than 2 years. It has been hypothesized that the physiological responses to chronically inflamed tissue results in higher concentrations of insoluble calcium carbonate to an injured area which contributes to the constant pain cycle and abnormal restructuring of myofascial tissue. The acetate ion in acetic acid combines with the calcium

ion in calcium carbonate to form more soluble calcium acetate, see blow chemical equation, which is then able to dissolve within local blood circulation and removed from the site of injury (**Costa & Dyson, 2007**)

## **CHAPTER III**

### **SUBJECTS, MATERIALS AND METHODS**

The current study will conducted to investigate the efficacy of Shockwave phonophoresis on calcaneal spur, this study will conducted at outpatient clinic in faculty of physical therapy at Beni-Suef University, Beni-Suef governorate, Egypt.

#### **1. Design of the study:**

Double-blinded pretest posttest randomized control design will used.

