#### **2. Subjects:**

The age of participant will range from 30 to 65 years. These patients will be allocated from the outpatient clinic in faculty of physical therapy at Beni-Suef University. The purpose, nature and potential risk of the study will be explained to all participant and they will sign a written informed consent prior to participation (**Appendix I**). Forty patients from both gender will be involved in this study and will randomly subdivided into two equal groups in number:

**Group (A):** (experimental group 1) this group composed of 20 subjects represented the experimental group 1. They will receive 6 sessions acetic acid shockwaves phonophoresis with Time between sessions 5-7 days plus exercise and dietary advice.

**Group (B):** (experimental group 2) this group composed of 20 subjects and represented the experimental group 2 who will receive 6 sessions of Shockwave plus exercise and dietary advice.

**Group (C): (Control Group):** This group composed of 20 subjects they will take conventional physical therapy program (Exercise)

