### **B. Therapeutic methods:**

#### **1. Shockwave therapy:**

- The shockwave will be applied for both group:
  - a. Group A: Shockwave (with 5% Acetic acid gel).
  - b. Group B: Shockwave (with ultrasound coupling medium gel).
  - c. Group C: conventional physical therapy program (Exercise).
- Once per week for 6 weeks for Shockwave.
- The intensity of Shockwave adjusted according to highest energy flux density the patient can tolerate. To achieve the best improvement in pain relief, the energy level of ESWT will adjusted to the maximum level that patients can tolerate the pain induced by ESWT
- Application at the most painful sit on Calcaneus.
- Total Energy flow density will calculated (as the product of the number of treatment sessions, the number of impulses per treatment session and the EFD of the impulses)(**Schmitz et al., 2015**).

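### The design is called double-blinded without naming who is blind; if exercise-only Group C is kept, participants cannot be blind in comparisons with it, and no masking of gels, assessors or x-ray readers is described

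*Combined protocol and SAP*

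**What the plan says.** Chapter III, section 1 (Design of the study) is one sentence: "Double-blinded pretest posttest randomized control design will used". It does not say which roles are blind, and blinding is not mentioned again in the available text.

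Section 2 (Subjects) opens with "Forty patients from both gender will be involved in this study and will randomly subdivided into two equal groups in number" and then lists three groups of 20. Group A has six sessions of shockwave with acetic acid gel. Group B is the group "who will receive 6 sessions of Shockwave plus exercise and dietary advice". For Group C: "This group composed of 20 subjects they will take conventional physical therapy program (Exercise". No sham shockwave is listed for C.

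Section 6.B (Shockwave therapy) says "The shockwave will be applied for both group" and then lists all three groups, the last as "Group C: conventional physical therapy program (Exercise". The comparator gel appears as "Group B: Shockwave (with ultrasound coupling medium gel", against 5% acetic acid gel in A. On intensity, the section says "the energy level of ESWT will adjusted to the maximum level that patients can tolerate the pain induced by ESWT".

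On outcomes, section 6.A has the patient mark the VAS, describes the FAAM as self-report, and takes the algometer reading at the point where the patient reports pain. Spur length and width are measured by computer on lateral x-rays. The section does not say who measures, or whether group or visit is hidden from that person.

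**The concern.** A double-blind label tells the reader that expectation and assessor judgement have been kept out of the comparison. Three of the four outcomes named in the Hypothesis section (pain intensity, physical function, PPT) depend on what the participant reports. A participant in an exercise-only group knows that no shockwave was given, and a participant treated at the limit of pain tolerance knows that it was. If C is in the trial, a difference from C on these outcomes that comes partly from expectation could be reported as double-blind evidence.

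Spur length does not depend on patient report. It can be protected from reader bias in every contrast, but only if the images are coded before they are measured, and the X-ray section does not provide for this.

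**Working it through.** The check is mainly a comparison of sections. The only arithmetic is counting.

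**1. Is Group C in the trial?**
- For two groups: the stated total is 40, and 2 × 20 = 40. The shockwave section refers to both groups. The research questions, aims and hypotheses state a between-treatment comparison only for A versus B.
- For three groups: Subjects and Shockwave therapy both list Group C, and 3 × 20 = 60. Kruskal-Wallis and Bonferroni pairwise comparisons in Statistical Analysis suit three groups.
- The documents do not settle it, so both cases are followed.

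**2. If C is kept, who can be blind?**
- A versus C and B versus C: C has exercise and no sham. A and B have six shockwave sessions at the maximum tolerated pain, and intact sensory perception is an inclusion criterion. Participants cannot be blind. An x-ray reader can be, and an algometer operator could be.
- A versus B: the treatments differ in the coupling gel, so participant blinding is feasible. Therapeutic Equipment and Shockwave therapy do not say that the gels look, smell or feel alike, or that the gel is concealed from anyone.

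**3. Which results are affected?** Take the four outcomes in the Hypothesis section (spur length, PPT, pain intensity, physical function).
- Three groups give 3 contrasts, so 3 × 4 = 12 contrast-outcome pairs.
- Contrasts with C on participant-reported outcomes: 2 × 3 = 6 of 12. Each would be assessed at posttest and at one month.
- Spur length: 3 × 1 = 3 of 12, all of which coded reading could protect.
- With two groups: 1 × 4 = 4 pairs. None is unblindable by design, and none has a described concealment.

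This is enumeration, not a measure of bias. No hypothesis is stated for A versus C or B versus C, and counting spur width or the two FAAM subscales separately would change the totals.

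**4. Who takes the assessor-dependent measurements?** The PPT section uses therapist and investigator for the person applying the algometer, and does not say whether that person treats the patient or knows the group. Because the operator controls how the force is raised, this matters in A versus B as well.

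**5. How many images would be coded?** The X-ray section requires at least two per patient: 40 × 2 = 80, or 60 × 2 = 120. If films are also taken at one month, the counts are 40 × 3 = 120 or 60 × 3 = 180.

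**The case against.** The strongest reply is that the label is not shown to be false. Double-blinded can mean two roles other than the participant, for example assessor and analyst, and the design section does not claim that participants are blind. This stands. A reader might infer that the plan contradicts itself on blinding; the documents support only that the blinded roles are unnamed and that participants cannot be among them in contrasts with C.

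Second, Group C may be a drafting remnant. This also stands as a possibility. A reader might infer that half of the planned comparisons are unblinded, but the 6 of 12 count applies only if C is kept, and the stated between-treatment hypothesis concerns A versus B alone. Dropping C does not remove the missing gel concealment or the missing image coding.

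Third, masking may be described on pages that were removed, such as the consent appendix. That is possible for the A versus B gels, so the finding is limited to the available text. No consent wording could make exercise feel like shockwave.

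Finally, a reader might infer that C is denied dietary advice and that differences from C are confounded by it. The documents do not establish this. Subjects lists the advice only for A and B, but Therapeutic Equipment and the Advices section list it without limiting it to any group. That is a separate inconsistency to reconcile and not a blinding matter.

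**Conclusion.** The concern holds in conditional form. The blinding claim names no roles and has no described procedure behind it. If Group C is kept, participants cannot be blind in A versus C or B versus C, and VAS, FAAM and PPT in those two contrasts rest on an unblinded participant's report. If C is dropped, participant blinding in A versus B is feasible but undocumented. In either case, no coded reading of the x-rays and no blinding of the algometer operator is described.

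This rests on two premises: that C receives no sham, as the text is written, and that the available methods sections are where masking would be stated. The direction and size of any bias cannot be derived from the documents. The point should be corrected before films are measured; it does not invalidate the trial.

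**What to change.** First reconcile Subjects and Shockwave therapy on two groups (40) or three (60). Then:

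1. **Design of the study.** Replace the unqualified label with the blinded roles for each contrast. If C is kept, state that participants are not blinded in A versus C and B versus C, and report VAS, FAAM and PPT differences from C as open-label for participants. For A versus B, keep a participant-blind label only if Therapeutic Equipment and Shockwave therapy state that the two gels are supplied so that the participant cannot tell them apart; otherwise drop it.
2. **X-ray.** Add: *Spur length and width are measured on coded images, with group hidden from the person measuring, and visit too where practical.* An existing team member other than the person measuring can do the coding.
3. **Pressure pain threshold.** State whether the person applying the algometer knows the group, and keep that person unaware of it where existing staffing allows.

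The cost is protocol wording and the coding of at least 80 images for 40 patients or at least 120 for 60. If C is kept, the design label becomes weaker. The blinding changes themselves alter neither treatment nor sample size.

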#### **2. Subjects:**

The age of participant will range from 30 to 65 years. These patients will be allocated from the outpatient clinic in faculty of physical therapy at Beni-Suef University. The purpose, nature and potential risk of the study will be explained to all participant and they will sign a written informed consent prior to participation (**Appendix I**). Forty patients from both gender will be involved in this study and will randomly subdivided into two equal groups in number:

**Group (A):** (experimental group 1) this group composed of 20 subjects represented the experimental group 1. They will receive 6 sessions acetic acid shockwaves phonophoresis with Time between sessions 5-7 days plus exercise and dietary advice.

**Group (B):** (experimental group 2) this group composed of 20 subjects and represented the experimental group 2 who will receive 6 sessions of Shockwave plus exercise and dietary advice.

**Group (C): (Control Group):** This group composed of 20 subjects they will take conventional physical therapy program (Exercise)

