## **Statistical Analysis:**

- All analysis will be carried out using the statistical package SPSS V.25.00 (IBM Corporation).
- Data will be expressed as mean and SD or median (in case of violation of normality) for continuous variables and as percentages for categorical data.
- The Shapiro-Wilks test will be used to test the normality of the data.
- 2-way mixed Design MANOVA will be used to compare the groups for normally distributed data.
- 2-way mixed Design MANOVA will be used to compare the groups for normally distributed data.
- Kruskal Wallis and Mann-Whitney tests will be used to compare the groups for non-parametric and not normally distributed data.
- Age and gender will be considered as an independent variable.
- Pairwise multiple comparisons will be performed using the Bonferroni correction test.
- All tests are two-sided, and statistical significance will be set at  $p<0.05$ .

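### The Subjects section randomises 40 patients into two equal groups, then lists three groups of 20, which makes 60

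*Combined protocol and SAP*

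**What the plan says.** The total and the allocation appear once, in Chapter III, section 2 (Subjects): "Forty patients from both gender will be involved in this study and will randomly subdivided into two equal groups in number". The same section then describes three groups:

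- Group A, acetic acid shockwave phonophoresis: "this group composed of 20 subjects represented the experimental group 1".
- Group B, shockwave alone: "this group composed of 20 subjects and represented the experimental group 2".
- Group C, labelled the control group: "This group composed of 20 subjects they will take conventional physical therapy program (Exercise".

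Section 1 (Design of the study) gives the design in one sentence: "Double-blinded pretest posttest randomized control design will used". Under Therapeutic methods, the Shockwave therapy section opens with "The shockwave will be applied for both group" and then lists A, B and "Group C: conventional physical therapy program (Exercise".

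The Statement of the Problems, the Purposes of study and the Hypothesis section each contain one explicit between-group comparison, A against B. Their other two items ask about the effect of each shockwave treatment without naming a comparator. The Statistical Analysis section says "Kruskal Wallis and Mann-Whitney tests will be used to compare the groups for non-parametric and not normally distributed data" and also plans Bonferroni-corrected pairwise comparisons.

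**The concern.** The sentence with the total and the list under it describe two different trials: one of 40 patients in two arms, the other of 60 in three. Someone preparing the randomisation could not tell how many allocations to generate, in what ratio, or when enrolment is complete.

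The status of Group C also decides what the trial can claim. The design is called randomised and controlled, and C is the only group labelled control. The list after the colon includes C, but a division into two groups leaves no place for it.

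- If C were recruited outside the allocation list, comparisons of A with C and of B with C would be open to selection bias.
- If C is not part of the trial, both remaining groups receive shockwave plus exercise and dietary advice. The first two null hypotheses would then rest on pre-post change alone, which cannot separate a shockwave effect from natural course or from the shared exercise and advice.

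**Working it through.** **Inputs, all from Chapter III, section 2 (Subjects):** stated total 40; stated number of groups 2, equal in size; Group A 20; Group B 20; Group C 20.

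**Step 1: reproduce the stated total.** Two equal groups out of 40 give 40 / 2 = 20 per group, which matches each listed group size. The total of 40 is therefore recovered from any two of the listed groups: A + B = A + C = B + C = 20 + 20 = 40.

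**Step 2: add up the list as written.** 20 + 20 + 20 = 60. The difference is 60 − 40 = 20 patients, and 20 / 40 = 50% of the stated total.

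**Step 3: try to keep 40 with three groups.** 40 / 3 = 13.3, not a whole number. The nearest split is 13/13/14, which is neither equal nor the stated 20 per group.

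**Step 4: look for a section that decides between the two versions.**

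| Section | Points to | Why it does not settle the matter |
|---|---|---|
| Subjects, opening sentence | 40 patients, two arms | Contradicted by the list that it introduces |
| Subjects, group list | 60 patients, three arms | Contradicted by the sentence above it |
| Design of the study | A control group | Gives no number of arms |
| Statement of the Problems, Purposes of study, Hypothesis | A against B explicitly | The two effect items name no comparator; they can mean A against C and B against C, or change within a group |
| Shockwave therapy | C is listed | The word both can refer to the two shockwave groups only |
| Statistical Analysis, Kruskal-Wallis | Three groups | An indication only; the test can be run on two groups, and a two-group test is named beside it |
| Statistical Analysis, Bonferroni | Several comparisons | Measurement methods sets three time points (before, after, and one month later), so these could be comparisons over time |

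No section gives a total of 60, a 1:1:1 ratio, or a non-randomised route for Group C. There is no sample size calculation, so a planned power or effect size cannot be used to work back to the intended total.

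**Step 5: which group could be surplus?** The arithmetic alone cannot say, because any pair gives 40. If one group is surplus, C is the most plausible: A and B are both labelled experimental, and theirs is the only comparison that the hypotheses spell out.

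**The case against.** The strongest reply is that the opening sentence is simply a leftover and that three arms are intended. Group C has its own label, size and treatment, it is listed a second time under Shockwave therapy, the design claims a control, and Kruskal-Wallis has little purpose with two arms. On this view the word both under Shockwave therapy correctly means A and B, since C receives no shockwave, and Mann-Whitney is the usual follow-up to an overall three-group test. Nothing suggests that C is recruited separately, so the selection-bias worry is hypothetical.

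Much of this is fair. The Shockwave therapy wording and the presence of Mann-Whitney are weak evidence of a second count of arms, and the conclusion needs neither. A leftover sentence is a credible explanation. But it is a guess at intent: the only total in the protocol is 40, the only stated allocation is into two groups, and the only explicit comparison is A against B. Treating C as a non-randomised addition does not rescue the text either. Forty randomised into A and B would then fit, but the same sentence says that forty patients are involved in the study, and 60 would be enrolled. The selection-bias point is conditional and is offered only as a consequence of leaving C's status open.

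**Conclusion.** The contradiction is real and must be fixed before an allocation list is drawn up. Firm: 60 patients against 40, a gap of 20 or 50% of the stated total; three groups against two; and no equal three-way split of 40. Not firm: which version was intended, and whether Group C is part of the randomisation.

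The conclusion rests on the Subjects section alone, where all the figures stand in continuous prose, and it needs no outside assumption. The statement that nothing else resolves it covers the protocol text apart from the title and consent pages, which were not available.

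**What to change.** State one total, one number of arms and one allocation ratio, and make the Statement of the Problems, Purposes of study, Hypothesis, Subjects, Shockwave therapy and Statistical Analysis sections agree. The choice belongs to the sponsor.

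1. **If three arms of 20 are planned.** In Subjects, write: *Sixty patients will be randomly allocated 1:1:1 to Groups A, B and C (20 each).* Put C in the same randomisation list. Name the comparator for each hypothesis (A–C, B–C, A–B) wherever the questions, aims and nulls appear. Reword the opening of the Shockwave therapy section to fit the three groups listed under it.
2. **If 40 patients in two arms are planned.** Remove Group C from Subjects and from Shockwave therapy, and Kruskal-Wallis from Statistical Analysis. State that the first two hypotheses concern pre-post change within each group. Check the design sentence as well, since no group labelled control would remain.

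If 40 patients in three arms is what is meant, the group sizes of 20 must change too, because the nearest split is 13/13/14.

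**Cost.** Wording only, with one exception. If 40 was the real target and three arms of 20 are kept, the trial gains 20 patients, at least 20 × 2 = 40 X-rays (at least two per patient, X-ray section) and 20 × 3 = 60 assessments (three per patient, Measurement methods).
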